5.10. Patient Lost to Follow Up

A patient will be considered lost to follow up and withdrawn from the registry once they have missed three consecutive follow-up visits or phone follow-up. Three documented attempts should be made by the investigator or designee to contact the patient or next of kin. One of the three documented attempts must include a certified letter.

5.11. Registry Participant Completion

An implanted patient has completed the registry once an element of the last requested follow-up visit has been performed or the collection of follow-up information would be outside of the visit windows. An implanted patient that does not complete these requirements due to voluntary withdrawal, physician withdrawal, death, or any other reason will be considered a withdrawal. Regular follow-up after registry completion is suggested to be conducted in accordance with the discretion of the site investigator or sub-investigator(s) and standard of care.

Patients will not be provided with any medical care by Gore after registry completion or withdrawal.

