### 3.2.3. Secondary Endpoint(s)

Selected events that are illustrative of the device's potential impact to a patient from a safety perspective, overall device function described as patency or device durability captured as device integrity are the registry's secondary endpoints. Possible endpoint events will be identified from site reports with some secondary endpoints within scope of CEC adjudication.

The secondary endpoints for the VBX 17-04 registry are the following:

- VBX Stent Graft-related death within 30 days post-treatment
- Procedural-related death within 30 days post-treatment
- Procedural-related SAE within 30 days post-treatment
- VBX Stent Graft patency (primary, primary assisted, secondary) through 30 days post-treatment
- VBX Stent Graft patency (primary, primary assisted, secondary) through five years post-treatment
- VBX Stent Graft-related SAE through five years post-treatment
- VBX Stent Graft-related death through five years post-treatment
- Loss of device integrity through five years post-treatment
- Limb salvage through five years post treatment

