#### 5.8. Follow Up

It is expected that implanted patients will be followed according to the standard practice of the enrolling physician. Accordingly, the registry will facilitate the collection of data obtained from physical examinations, medication use, and imaging assessments for multiple types of imaging modalities (*e.g.,* CTA or ultrasound). For the purpose of registry reporting and eCRF organization, it is expected that most implanted patients will have a clinical follow-up visit within 1-3 months of the procedure with the next follow-up or device evaluation at approximately 9-12 months post-procedure. Thereafter follow-up will continue annually until 5 years post-procedure. The frequency of implanted patient evaluations and the imaging modality used to investigate treatment and device status is up to the discretion of the follow-up physician. In some cases (i.e. patient unable to reach the hospital) a phone follow-up can be acceptable as a visit.

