### 5.8.1. Follow-Up Visit Windows

To aid in registry reporting, collected data will be organized and categorized into six visits. **Table 3** describes the range of days where collected data will be assigned to either visit type. Any evaluation of the VBX Stent Graft outside of the general reporting windows can be entered in the EDC system as an unscheduled visit.

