Analysis of the secondary endpoints—device related death at 30 days, procedural related death at 30 days, procedural related SAE at 30 days, device patency at 30 days, in addition, device patency, device-related SAEs, device related deaths and loss of device integrity will be reported yearly as both yearly percentages and rates. Data will be presented descriptively with 95% confidence intervals, where appropriate. Subjects with missing information on these outcomes will not be included in the analysis.

vi) Analysis by Treatment Category

Individual device treatment indications will be categorized into larger groups "Treatment Categories" based upon either similar device function or purpose. Combining treatment indications into larger groups will permit the analysis of general treatment concepts where an analysis based upon an individual indication would not be feasible. Analyses of a Treatment Category will be performed descriptively with no pre-determined hypothesis.

vii) Analysis of Individual Treatment Indications

At the conclusion of enrollment, an evaluation of the distribution of device use across individual pathologies will be performed. If feasible, device experience by indication will be tabulated for descriptive analysis.

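### Protocol 5.10, 5.11 and SAP 6.0 i conflict: a patient last seen at year 3 or 4 can never be declared lost to follow-up and, read literally, is classed as having completed the registry without any year-5 contact

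*Protocol*

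**What the plan says.** **Schedule.** Protocol 5.8 describes the first contact in these words: "most implanted patients will have a clinical follow-up visit within 1-3 months of the procedure". It places the second at roughly 9 to 12 months. For the later years it says: "Thereafter follow-up will continue annually until 5 years post-procedure". Protocol 5.8.1 says that "collected data will be organized and categorized into six visits". In some cases a phone contact may stand in for a visit (5.8).

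**Loss to follow-up.** Under Protocol 5.10 a patient is lost, and thereby withdrawn, "once they have missed three consecutive follow-up visits or phone follow-up". Three documented contact attempts are also required, one of them a certified letter, but no timing is given for them.

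**Completion.** Protocol 5.11 gives two alternative routes. Either some part of the final requested visit has been carried out, "or the collection of follow-up information would be outside of the visit windows". A following sentence treats a patient who does not meet these requirements, for whatever reason, as a withdrawal. Death is named there as a withdrawal, as it is in 5.9. Loss to follow-up is not in the list of withdrawal reasons in 5.9.

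**Analysis.** SAP 6.0 i starts the final analysis once every subject has either had the 5-year visit or been withdrawn. The secondary endpoints include "VBX Stent Graft-related SAE through five years post-treatment" (Protocol 3.2.3), with matching endpoints for device-related death and limb salvage. SAP 6.0 v says that device patency, device-related SAEs, device-related deaths and loss of integrity "will be reported yearly as both yearly percentages and rates", and leaves out subjects whose outcome information is missing.

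**The concern.** Three rules meet at the end of follow-up and do not agree. The loss rule counts missed visits, and near the end of the schedule too few visits are left to count. The second route to completion in 5.11 asks for no contact and no data, only that the window has passed. The SAP trigger knows only two states, and a patient silent since year 3 or 4 is in neither unless somebody chooses to withdraw that patient.

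The first thing at stake is disposition. The number reported as completing the registry can include patients whom nobody contacted in the last one or two years.

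The second is the late safety figures. Possible SAEs and deaths are identified from site reports, so a silent patient produces no event record. The visible SAP text does not say what counts as missing for an event endpoint, nor when observation ends for the yearly percentages and rates. A patient labelled as a completer with no event form could therefore be carried as event-free.

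**Working it through.** **Step 1. Reproduce the visit count.** From Protocol 5.8: 1-3 months, 9-12 months, and years 2, 3, 4 and 5. That is 2 + 4 = 6, which agrees with the six visits in 5.8.1.

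**Step 2. Apply the three-miss rule (5.10) to each possible last visit.**

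| Last seen | Scheduled visits left | Third consecutive miss falls at |
|---|---|---|
| Procedure / discharge | 6 | year 2 |
| 1-3 months | 5 | year 3 |
| 9-12 months | 4 | year 4 |
| Year 2 | 3 | year 5 |
| Year 3 | 2 | never |
| Year 4 | 1 | never |

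The result does not depend on the day ranges in Table 3, which are not shown in the public text. Only the number of remaining visits matters.

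**Step 3. Apply 5.11 when the year-5 window closes.** Patients last seen at year 3 or 4 have not met the loss rule, but they do meet the window-expiry route to completion. A patient last seen at year 2 reaches the third miss only when the year-5 window closes, so 5.10 (lost, withdrawn) and 5.11 (completed) apply at the same moment and give opposite labels.

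**Step 4. Compare with SAP 6.0 i.** A patient last seen at year 3 or 4 has not had the 5-year visit. Nothing in the protocol requires that patient to be withdrawn; 5.9 only permits the investigator to do so.

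**Step 5. Illustrate the size.** The documents give no drop-out figure. Assume that a constant fraction d of those remaining drops out each year, all of it silently. The number seen at year t is 280 × (1 − d)^t.

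| | d = 5% | d = 10% |
|---|---|---|
| Seen at year 3 | 240.1 | 204.1 |
| Seen at year 4 | 228.1 | 183.7 |
| Seen at year 5 | 216.7 | 165.3 |
| Last seen at year 3 | 12.0 | 20.4 |
| Last seen at year 4 | 11.4 | 18.4 |
| Labelled completed without year-5 contact | 23.4 | 38.8 |
| Completion with year-5 contact | 216.7/280 = 77.4% | 165.3/280 = 59.0% |
| Completion under literal 5.11 | 240.1/280 = 85.7% | 204.1/280 = 72.9% |
| Unobserved patient-years, years 4-5 | 2 × 12.0 + 11.4 = 35.4 | 2 × 20.4 + 18.4 = 59.2 |

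The year-2 group, whose label is ambiguous, is left out of these counts.

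**Step 6. What follows only if silent patients were counted as event-free.** The year-5 denominator would be 240.1 instead of 216.7, or 204.1 instead of 165.3. An assumed true yearly event percentage of 2% in year 5, with equal risk in seen and unseen patients, would then read 2% × 216.7/240.1 = 1.8%, or 2% × 165.3/204.1 = 1.6%.

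**The case against.** The best defence is that 5.11 is being read too literally. Taken at its word, the window-expiry route is eventually met by everyone, including patients who died or withdrew, and that would leave the sentence on withdrawals with nothing to do. A narrower meaning was probably intended. SAP 6.0 i points the same way: with only two states allowed, a silent patient would have to be withdrawn, and 5.9 lets the investigator do that at any time. This shows that a sensible intention is plausible. It does not remove the conflict, because withdrawal under 5.9 is discretionary and the sentence in 5.11 reaches only patients who meet neither route.

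A reader might infer that the unobserved years are in fact counted as event-free, so that late device-related SAE and death figures are biased downwards. The documents do not support that. No text ties the completion label to an endpoint denominator. Both documents exclude missing data, and data are assigned to visit windows, so an absent year-5 visit can be identified. The Table 3 ranges and the content of the SAP's dataset and table specifications are not visible in the public text, and a denominator rule could sit there. The bias is possible, not shown.

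It is also fair to object that the illustration treats all drop-out as silent. Deaths, explants, bypassed devices, and voluntary or investigator withdrawals are recorded as withdrawals under 5.9 and would not be mislabelled. The figures for patients last seen at year 3 or 4 are therefore upper bounds at the assumed drop-out.

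Finally, a reader might infer that every loss takes three years to be recognised. It does not: a patient never seen after discharge meets the rule at about year 2.

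**Conclusion.** The conflict is established by counting and by comparing the texts. The loss rule cannot fire for a patient last seen at year 3 or 4, it coincides with completion for one last seen at year 2, and literal 5.11 gives a label that SAP 6.0 i does not recognise for these patients.

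The direct consequence is that reported completion can be overstated, by at most about 8 percentage points at 5% yearly drop-out and 14 at 10% for the year-3 and year-4 groups. Those drop-out rates are assumptions, and the real effect is smaller to the extent that drop-out is recorded as withdrawal. Up to 35-59 patient-years in years 4-5 would have no observation behind them; how the analysis would treat them is left open.

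The 30-day primary endpoint is not touched, and the registry tests no hypothesis. The point is still worth correcting, because safety through five years is a stated aim and the correction is cheap.

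**What to change.** 1. **Protocol 5.11.** Delete the window-expiry route. Completion then requires a documented visit or phone contact in the year-5 window. A patient without one when that window closes is lost to follow-up, and so a withdrawal, as of the last documented contact. Death stays a withdrawal, as 5.9 and 5.11 already have it.
2. **Protocol 5.10 and 5.9.** Keep the three-miss rule for earlier loss. Add that closure of the year-5 window without contact also triggers loss to follow-up, and add loss to follow-up to the withdrawal reasons in 5.9. Lowering the threshold to two misses would not be enough, since a patient last seen at year 4 has only one visit left.
3. **SAP 6.0 v.** For device-related SAE, device-related death and limb salvage, state that observation ends at last documented contact or death, and that a patient with no earlier event and no contact in or after a yearly window counts as missing for that year. Limb salvage has to be named, because the present list of yearly outcomes in that section omits it.

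The cost is wording in two documents. No new procedure is imposed, since phone contact can already count as a visit. The downside is a lower reported completion rate and smaller denominators in the late years.

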5.12. Explant Procedures

### 6. Registry Administration

6.1. Training

All investigators were selected for their education, medical background, and proficiency with endovascular techniques as determined by the sponsor during the qualification process.

Prior to the start of enrollment, Gore will provide appropriate training to the investigator and their pertinent delegated staff members. Registry training will include:

- Registry protocol
- EDC system

Registry device is already marketed; therefore, specific device training for investigator and site staff will not be required.

6.2. Monitoring

Site monitoring for this protocol will be provided by a Contract Research Organization (CRO). Monitoring oversight will be provided by the sponsor. Sites must provide adequate access to all source data for the sponsor or representatives.

The site monitors are qualified by training and experience to oversee the progress of the registry at the site and will verify that the investigators and their staff understand and adhere to both the applicable regulatory requirements and the registry protocol. In addition, they may assist in resolution of any problems that may arise during the conduct of the registry.

6.2.1. Site Initiation

Site initiation will be performed to verify that each investigator and his / her staff understands the protocol, applicable regulations, human patient protection requirements, and the investigator's obligations. This visit will confirm that required documentation with the appropriate approval is in place prior to patient enrollment.

The clinical investigation shall not begin until the sponsor has confirmed the required approval / favorable opinion from the EC or regulatory authority has been obtained.

6.2.2. Periodic Site Monitoring

Periodic site monitoring will occur as necessary to verify continuing adequacy of facilities and adherence to the registry protocol, Good Clinical Practices (GCPs), and applicable regulations and laws that pertain to the conduct of the registry. These activities will also review the eCRFs and source documentation, the timely submission of accurate records to the sponsor, and the maintenance of proper records. A report will be written following each site visit and a follow-up letter will be provided to the site with a summary of findings. A close out visit will be conducted at each site to confirm that all documentation is complete.

in a clinical monitoring plan developed and maintained by Gore.

6.2.3. Device Accountability and Storage

Information on Gore accessory devices used during the procedure may be collected. This may include additional non-VBX Stent Graft devices, balloon catheters, and sheaths.

#### 6.3. Protocol Deviations

A protocol deviation is defined as any change, divergence, or departure from the registry design or procedures of a protocol. The investigator is responsible for promptly recording and reporting protocol deviations to Gore and the reviewing EC per their policy.

The investigator will not implement any changes to the protocol without first obtaining written agreement from the sponsor and documented approval from the EC, except in the event of an immediate hazard(s) to a patient.

For the purpose of this registry, as implant procedures and follow-up visits will be performed according to participating sites' standard practice, protocol deviations would only affect the informed consent signature process, verification of inclusion / exclusion criteria and data entry as specified in **Section 7.3**.

Gore will determine the impact of the protocol deviation on patient safety and determine if additional reports or actions are required. Additional action may include site retraining and / or site termination.

6.4. Protocol Amendments and ICF Revisions

The protocol and ICF may be amended by Gore throughout the life of the registry, as a result of new findings or business interests or needs. Investigators will obtain EC approval on all amendments in a timely manner. Gore will confirm proper training of investigators and site staff on all protocol amendments.

6.5. Sponsor Representatives

Gore representatives may be present during implant procedures to provide technical assistance to the investigator in the use of the device. The activities of the Gore representatives will be supervised by the investigator. Representatives may also assist in film reading, case planning, or training of site staff.

6.6. Access to Source Data / Documents

Source data are defined as all information necessary for the reconstruction and evaluation of the registry.

The investigator will keep all study records, source data, and registry devices available for inspection by Gore, its monitors, representatives of the EC, or regulatory authorities as required by local regulations. The investigator should maintain adequate and accurate source documents and registry records that include all pertinent observations on each registry patient. Source data should be attributable, legible, contemporaneous, original, accurate, and complete. When a copy is used to replace an original document, the copy should fulfill the requirements for certified copies. Changes to source data should be traceable, should not obscure the original entry, and should be explained if necessary (*e.g.,* via an audit trail).

### 6.7. Registry Records Retention

The investigator will maintain complete accurate and current study records as required by applicable regulatory requirements.

In any event, registry records will not be disposed of, nor custody of the records transferred, without prior written sponsor approval.

Investigator records will include, but not be limited to:

- All correspondence with another investigator, an EC, the sponsor, a monitor, or regulatory authority, including required reports.
- Records of each patient's case history and exposure to the device. Case histories
  include the CRFs worksheets and supporting data including, for example, signed and
  dated consent forms and medical records, including, for example, progress notes of the
  physician, the individual's hospital chart(s), and the nurses' notes. The protocol, any
  amendments, and documentation of any deviations from the protocol, including the
  dates and the reasons for such deviations.
- Any other records that regulatory authorities require to be maintained by regulation or by specific requirement for a category of investigations or a particular investigation.
- A signed Investigator Agreement.
- Any other records as required by the regulatory authority, the EC, and the sponsor.
- 6.8. Publication Plan

The International Committee of Medical Journal Editors (ICMJE) member journals have adopted a trials-registration policy as a condition for publication. This policy requires that all clinical trials be registered in a public trials registry. Gore will register the study and post results as required by this policy and applicable regional laws and regulations.

It is the intent of Gore that the multicenter results of this registry will be submitted for publication (in a peer reviewed journal).

Individual sites should coordinate requests for publication through the publications committee or Gore.

#### 7. Data Collection and Submission

The Clinical Data Management System (CDMS) for this registry will be provided by Medidata Solutions Worldwide, Inc. Gore keeps a separate Clinical Data Management Plan describing the procedures for verification, validation, and security of the CDMS. The Clinical Data Management Plan will describe and document procedures regarding data management processes for this investigation.

#### 7.1. Data Collection Methods

This registry will report clinical data using the Medidata Rave® CDMS web-based application. The CDMS will be the database of record for the protocol and patients to regulatory inspections and quality assurance review. All users will be trained to use the CDMS and will comply with registry-specific guidelines/instructions as well as applicable regulatory requirements.

Patient data will be collected using protocol-specific eCRFs. Site staff will enter data directly into the eCRF for transmission to the sponsor. The sites will be notified of any significant amendments to the eCRFs.

7.2. Data Clarification and Correction

Once entered, data will be evaluated to confirm that it is complete, consistent, and logically sound. If changes to the data in the CDMS are required, all changes, reasons for changes, and persons making the changes will be captured in the CDMS's audit trail. Gore will perform periodic data reviews throughout the term of the registry. Procedures and documentation for regular and ongoing data review are described in the Clinical Data Management Plan.

### 7.3. CRF Completion Schedule

Entry of patient data into the EDC system cannot occur prior to the collection of the patient's informed consent to participate in the registry. All registry data are targeted to be entered into the appropriate eCRF within 14 days of collection, however, data outside this window will not be considered a protocol deviation.

#### 8. Risk Assessment

A complete listing of the known risks associated with the VBX Stent Graft can be found in both the IB and IFU. Investigators are advised to review both documents to familiarize themselves with these risks and correlate this information with the patient's presenting pathology and prior medical history.

8.1. Summary of Expected Benefits

The VBX Stent Graft is a CE-marked device indicated for the endovascular grafting of peripheral vessels. Registry participants are expected to be suffering from a medical ailment where treatment with the VBX Stent Graft may alleviate patient symptoms, maintain vessel patency, or prevent a medical event associated with significant morbidity or mortality.

Participation in this observational registry is not expected to provide any direct benefits to participating patients, other than those related to the treatment of their pathology. However, the data collected during the registry will foster a better understanding of the performance of the registry devices in real world, daily application.

Moreover, as the registry will not require the use of any procedure and / or test and / or device different from those required by routine clinical practice for the investigated conditions, enrolled patients will not be exposed to additional risks as compared to routine clinical practice.

